9.3 Efficacy Assessment

9.3.1 Primary Efficacy Analysis

The primary outcome is the treatment success, which is defined as an increase in plasma glucose (PG) to \geq 70 mg/dL or an increase of \geq 20 mg/dL from PG nadir within 30 minutes after receiving glucagon, without receiving additional actions to increase the PG concentration. The nadir is defined as the minimum PG concentration at the time of or within 10 minutes following glucagon administration.

The primary analysis will be a treatment group comparison of the primary outcome in the EAS. The percentage of patients achieving treatment success in each treatment group and the difference in percentages will be computed. A 2-sided 95% CI will be obtained from the 1-sample mean of the paired differences in primary outcome (1 = outcome observed; 0 = outcome not observed) across 2 treatment visits. Noninferiority of nasal glucagon (NG) will be declared if the upper limit of a 2-sided 95% CI constructed on the difference in percentages (IMG minus NG) is less than the noninferiority margin of 10%. Specifically, for each patient, the paired difference of treatment success between IMG and NG will be calculated and PROC TTEST will be used to create the 95% CI of the mean difference.

Primary efficacy analysis will only include patients who complete both treatment visits with evaluable primary outcome. The analysis will be performed separately for each diabetes type. The following will be considered as nonevaluable primary efficacy outcome and excluded from the analysis related to primary efficacy outcome:

Final, 01 Feb 2018 Page 10 of 26

- Patients with at least 1 treatment visit in which the nadir PG is \geq 70 mg/dL;
- Patients receiving an external measure to raise PG concentration either before glucagon administration or within the first 10 minutes after glucagon administration.

Plasma glucose concentrations assessed through a central laboratory will be used to assess treatment success.

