9.3.2 Additional Analyses Related to Primary Efficacy Outcome

For each of the following populations, the proportion of patients achieving treatment success will be summarized for each treatment group and diabetic type, and compared using the same method as for the primary efficacy analysis specified above.

- ARS
- Patients in EAS population with nadir glucose <50 mg/dL on both treatment visits.

Among patients who achieve treatment success, the proportion of patients achieving (1) an increase in glucose to \geq 70 mg/dL, or (2) an increase of \geq 20 mg/dL from nadir, or (3) an increase in glucose to \geq 70 mg/dL and an increase of \geq 20 mg/dL from nadir will be summarized for each treatment group and compared using the same method as for the primary efficacy analysis specified above for all 3 populations (ie, EAS, ARS, and EAS with nadir \leq 50mg/dL on both treatment visits).

As an additional sensitivity analysis, in the EAS population, the primary efficacy outcome will be assessed by comparing the upper limit of a 2-sided 95% CI on the difference in proportions obtained from a Poisson regression model using the binary primary outcome, accounting for the correlation due to the cross-over design using a generalized estimating equation. The model will include adjustments for nadir glucose level and treatment period.

Below is the example SAS code computing the treatment difference in proportion of patients achieving treatment success and 95% CI using the Poisson regression model:

```
proc genmod data=a;
class visit treatment patient;
model success = treatment visit nadir / dist=poisson link=identity;
repeated subject=patient / type=un;
estimate 'success' treatment 1 -1;
lsmeans treatment / diff cl om;
run;
```

The time from study drug administration to achieve treatment success will be summarized. A Kaplan-Meier (KM) analysis will be used to analyze the time from study drug administration to achieve treatment success. If both components of the treatment success (ie, an increase in glucose to \geq 70 mg/dL and an increase of \geq 20 mg/dL), are achieved for a patient, the earlier time point will be used. If a patient receives an external measure to raise glucose at any point, right censoring will be used. A treatment group comparison of the time to achieve treatment success

Final, 01 Feb 2018 Page 11 of 26

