will be performed using Cox proportional hazard models accounting for the correlation due to the crossover design, adjusted for baseline glucose value and treatment period. Due to the discrete time data (5-, 10-, or 30-minute intervals), the exact method will be used. This method averages the Cox proportional hazards likelihood over all possible orderings of tied event times.

In addition, time to achieving either an increase in glucose to \geq 70 mg/dL or an increase of \geq 20 mg/dL from nadir will also be analyzed, separately, using the KM estimator of the survival function.

Below is the example SAS code creating KM life table and curve by treatment group:

```
proc lifetest data=b plots=(s) outsurv=kmtable;
time minutes*censor(1);
strata treatment;
run;
```

Below is the example SAS code using proportional hazard model:

```
proc phreg data=b covs(aggregate);
id patient;
class treatment visit;
model minutes*censor(1) = treatment visit nadir / ties=exact;
run;
```

For the time to event analysis, if a patient receives additional intervention treatment to raise glucose prior to achieving a glucose value ≥ 70 mg/dL or an increase of ≥ 20 mg/dL from nadir, the remaining time points will be considered as non-events (ie, glucose is not ≥ 70 mg/dL and does not increase ≥ 20 mg/dL from nadir).

The time to treatment success analysis will also be repeated in EAS patients with nadir glucose value <50 mg/dL.

A complete by-patient listing of primary efficacy data will be created.

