9.5 Pharmacodynamic Assessment

9.5.1 Pharmacodynamic Analysis

Pharmacodynamic parameters will be calculated using NCA Drug Effect Model in validated software program (Phoenix WinNonlin Version 6.4.1 or later) and/or SAS. Key PD parameters will be derived to assess the exposure to glucose and duration of exposure above, below, and within the normal glucose range. The normal range for PG will be considered to be 70 to 108 mg/dL. Actual sampling times will be used for all calculations.

The following PD parameters will be calculated using concentrations of glucose:

Final, 01 Feb 2018 Page 16 of 26

Parameter	Definition
AUECabove	Area under the effect concentration-time curve above the normal range
$AUEC_{below}$	Area under the effect concentration-time curve below the normal range
$AUEC_{within}$	Area under the effect concentration-time curve within the normal range
$AUEC_{0-1.5}$	Area under the effect concentration-time curve from time zero (predose) up to 1.5 hours
BG_{max}	Maximal blood glucose
Duration _{above}	Duration above normal range
Duration _{below}	Duration below normal range
Duration _{within}	Duration within normal range
t_{above}	Time to concentrations above normal range
$t_{ m below}$	Time to concentrations below normal range (after t _{above})
t_{within}	Time to concentrations within normal range
T_{max}	Time to maximum concentration

The following PD parameters will be calculated using baseline-adjusted (ie, change from baseline) concentrations of PG: AUEC_{0-1.5}, BG_{max}, and T_{max}.

Baseline PG concentrations will be concentrations from samples obtained immediately prior to glucagon dosing (ie, time point of 0.00 hour).

If a patient receives additional intervention to raise PG concentrations, measurements taken after the time of intervention will be excluded from the estimation of PD parameters.

Other PD parameters of PG may be calculated if required. Individual concentrations and PD parameters of PG will be summarized with descriptive statistics by treatment.

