9.5.3 Plasma Glucose Values Statistical Methodology

Descriptive statistics will be used to summarize the baseline, various postdose time points (15, 30, 45, 60, and 90 minutes post glucagon administration), and absolute change from baseline in PG values by treatment group for the FAS.

If a patient receives additional intervention to raise PG concentrations, measurements taken after the time of intervention will be excluded from the analysis.

For this analysis, baseline is defined as the last nonmissing PG measured at the time of or immediately prior to glucagon administration at each treatment visit. A treatment comparison of glucose over the 90 minutes following administration of glucagon will be completed using a linear mixed model with repeated measures (MMRM) that accounts for the correlation due to the crossover design and the correlation due to multiple measures. The baseline score, treatment period, time points and their interaction will be included as covariates in the model. Least-square means and 2-sided 95% confidence limits will be calculated for the difference in PG between treatment groups (IMG minus NG) at each time point.

In the MMRM model, the within-patient errors are modelled as an unstructured variance-covariance matrix. If the analysis fails to converge, the following variance-covariance matrix will be used (in the order listed) until one converges:

- 1. Heterogeneous Toeplitz (TOEPH)
- 2. Heterogeneous First-order Autoregressive (ARH[1])
- 3. Heterogeneous Compound Symmetry (CSH)
- 4. Toeplitz (TOEP)
- 5. First-order Autoregressive (AR[1])
- 6. Compound Symmetry (CS)

The Kenward-Roger approximation will be used to estimate denominator degrees of freedom for the MMRM models.

Below is the example SAS code performing the MMRM analysis:

```
proc mixed data=c;
class patient time visit treatment;
model value = treatment time visit baseline treatment*time /solution
ddfm=kr;
repeated time(visit)/subject=patient type=un;
lsmeans treatment*time/cl diff om;
run;
```

As an exploratory analysis and if there is sufficient data, a subgroup analysis of plasma glucose over time by concomitant oral diabetes drug will be performed (with particular focus on Sulfonylureas). The purpose of the analysis is to assess whether the concomitant oral diabetes

Final, 01 Feb 2018 Page 18 of 26

drug triggers rebound hypoglycaemia or not. For each concomitant oral diabetes drug, the data will be summarized by treatment and diabetes type.

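### Time to treatment success (SAP 9.3.2): the Cox text adjusts for baseline glucose, but the example PHREG code fits nadir, which is partly post-dose

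*SAP*

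**What the plan says.** SAP 9.3.2 plans a Kaplan-Meier analysis of time from dosing to treatment success and a Cox comparison of treatments. The Cox model allows for the crossover correlation and is "adjusted for baseline glucose value and treatment period". The example PHREG statement that follows is "model minutes*censor(1) = treatment visit nadir / ties=exact". It has no baseline term.

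SAP 9.3.1 says: "The nadir is defined as the minimum PG concentration at the time of or within 10 minutes following glucagon administration". Section 9.3.2 does not define baseline. Where the SAP does define it for PG, it is the predose value: in 9.5.3, "baseline is defined as the last nonmissing PG measured at the time of or immediately prior to glucagon administration", and in 9.5.1 the sample at time zero.

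For the Poisson sensitivity model in the same section, text and code agree: "The model will include adjustments for nadir glucose level and treatment period", and the GENMOD code fits nadir.

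Two sentences cover patients given something to raise glucose. One says "If a patient receives an external measure to raise glucose at any point, right censoring will be used". The other says that, when this happens before success, "the remaining time points will be considered as non-events". No end of follow-up is stated for the time-to-event analyses.

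**The concern.** A programmer following the text and one following the code would fit different models, and the SAP does not say which governs. The difference matters because predose PG is fixed before treatment and nadir is not. If one product starts to act later, PG falls further before it turns, so the nadir is lower on that product. Adjusting for nadir then removes part of the onset difference that the analysis is meant to show. Nadir also overlaps the first 10 minutes at risk and enters the outcome through the +20 mg/dL criterion.

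The earlier crossover study gives a reason to care. In Protocol 3.2, participants with nadir below 50 mg/dL had a mean time to success of 16 minutes with nasal and 13 minutes with intramuscular glucagon. That does not show whether the delay was later onset or slower rise.

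If this stays open, the covariate and the time horizon could be chosen after open-label results have been seen.

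**Working it through.** **Covariate.** The four statements in SAP 9.3.2, side by side:

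| Model | Text | Code |
|---|---|---|
| Poisson | nadir, period | nadir, visit |
| Cox | baseline glucose, period | nadir, visit |

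Only the Cox row conflicts. By the SAP's own definitions, baseline is PG at time 0 and nadir is the minimum over 0 to 10 minutes, which on the protocol schedule means the 0, 5 and 10 minute samples. The two coincide only when the minimum falls at time 0.

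**Size.** The documents give no glucose profiles, so every input here is an assumption. Patient mean PG is N(52, 6) mg/dL with between-visit SD 3. PG falls 0.6 mg/dL/min until onset (SD 1.5 min), then rises 2.2 mg/dL/min (log-SD 0.25), with noise SD 1.5. Samples are every 5 minutes to 30 and the horizon is 30 minutes. Success is PG at least 70 mg/dL or at least 20 above nadir. The Cox model has treatment, period and one glucose covariate, with exact ties. There were 400 trials of 66 pairs per scenario. Hazard ratios (HR) are nasal to intramuscular. The last columns give the median, and where available the 5th to 95th percentile, of the within-trial ratio (nadir-adjusted over baseline-adjusted).

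| Assumed scenario | HR, baseline | HR, nadir | Ratio | 5th–95th |
|---|---|---|---|---|
| Onset 5 (IM) vs 8 min (nasal) | 0.348 | 0.379 | 1.082 | 1.014–1.198 |
| Same, no fall before onset | 0.353 | 0.360 | 1.021 | – |
| Same, fall 1.0 mg/dL/min | 0.342 | 0.389 | 1.115 | – |
| Onset 5 vs 6.5 min | 0.593 | 0.614 | 1.042 | 0.978–1.117 |
| Equal onset, rise 2.2 vs 1.7 | 0.456 | 0.449 | 0.984 | 0.898–1.057 |
| No treatment difference | 1.012 | 1.015 | 1.000 | 0.932–1.082 |

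The mechanism shows in the mean fall from predose to nadir (IM vs nasal): 2.1 vs 3.7 mg/dL at onset 5 vs 8 min, 2.1 vs 3.0 at 5 vs 6.5, and 2.1 vs 2.2 at equal onset with slower rise.

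A second simulation used different assumed curves, Efron ties and a nasal onset 3 minutes later. It moved the HR the same way: 0.547 to 0.596 at a 30-minute horizon and 0.581 to 0.630 at 90 minutes.

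For scale, in the first row the log shift is ln(0.379/0.348) = 0.085. With about 2 × 66 = 132 events, a rough unpaired standard error of the log HR is 2/√132 = 0.17. The shift is about half a standard error.

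**Horizon.** PG times after dosing in the protocol schedule are 5, 10, 15, 20, 25, 30, 40, 50, 60, 90, 120 and 240 minutes. The gaps are six of 5 minutes (to 30), three of 10 (to 60), two of 30 (to 120) and one of 120 (to 240). The ties sentence in 9.3.2 names gaps of 5, 10 and 30 minutes. That set fits follow-up to 90 or 120 minutes. It does not fit 30 minutes (5-minute gaps only) or 240 (which adds a 120-minute gap). Success in 9.3.1 is nevertheless defined within 30 minutes.

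The earlier study shows the consequence. Nasal success at 30 minutes was 74/75 = 98.7%, and the remaining patient met both criteria at 40 minutes. With no rescue, that patient is censored at a 30-minute horizon and is an event at a later one (75/75 = 100%). This changes the Kaplan-Meier curve as well as the Cox model.

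**Rescued patients.** Right censoring most naturally means leaving the risk set at the time of rescue. Treating later time points as non-events keeps the patient at risk to the end of follow-up, which is not stated. Protocol 9.2.4 lets IV glucose depend on readings at 30 and 45 minutes, so a horizon past 30 minutes makes the choice relevant.

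**The case against.** The code is labelled as an example. On an ordinary reading the prose specifies the model, and the mismatch is then editorial. That is plausible, but the SAP gives neither precedence, and Protocol 10.3.1.1 leaves additional analyses to the SAP, so nothing else resolves it.

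The stray word might instead be baseline. Section 9.3.2 does not define it, the definitions in 9.5.1 and 9.5.3 belong to other analyses, and the other three statements in 9.3.2 all say nadir. It is true that editing the text would also remove the conflict. The preference for predose PG rests on two things: it is what the prose says, and it is the only one of the two that treatment cannot affect.

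The Poisson model adjusts for the same nadir. A reader might infer that it is wrong as well. Its text and code agree, so there is no inconsistency there. Whether nadir is a good covariate in that model is a separate question of choice.

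The shift is small and its size is invented along with the curves. This stands. In the two scenarios with onset 5 vs 6.5 minutes or slower rise alone, the percentile range of the ratio includes 1, and with slower rise the median shift is slightly away from 1. No scenario is shown to change a conclusion.

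On the horizon, the definition of success could be taken to fix 30 minutes already. The wording on intervals makes that uncertain but does not contradict it outright, so this part is only a request for clarification.

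**Conclusion.** The Cox text and the example code name different covariates, and the one in the code is partly post-dose. This should be corrected before analysis. The effect is confined to a supportive Cox model and its repeat in patients with nadir below 50 mg/dL. On the assumed profiles the hazard ratio moves modestly towards 1 if nasal onset is later (ratio 1.02 to 1.12) and hardly at all otherwise (0.98 to 1.00). The existence of the conflict rests on the SAP text alone; its size rests wholly on assumed curves.

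Three stronger readings are tempting and are not supported:
- That the non-inferiority result is at risk. The primary analysis is a paired-difference confidence interval that uses neither baseline nor nadir as a covariate.
- That nadir always differs from baseline. Its window includes time 0.
- That the two rescue sentences, read together, mean censoring at the horizon, or that they flatly contradict each other. They can be read either way, and the documents do not settle which is meant.

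**What to change.** In the PHREG example, replace nadir with predose PG, and add a sentence to SAP 9.3.2 saying that baseline there has the 9.5.3 definition.

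As clarifications in the same paragraph:
- State the time-to-event horizon for both the Kaplan-Meier and Cox analyses, either the 30 minutes of the success definition or a named later sampling time, and say that patients with neither success nor rescue are censored then.
- Reconcile the two statistical rules for rescued patients by stating one censoring time. The sponsor has to decide which was meant.

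The cost is one code term and a few sentences. Predose PG is already collected in each period, and the sample size and primary analysis do not change.

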9.4 Pharmacokinetic Assessment

9.4.1 Pharmacokinetic Analysis

Pharmacokinetic parameter estimates will be determined using non-compartmental procedures in validated software program (Phoenix WinNonlin Version 6.4 or later).

Plasma concentrations of glucagon will be used to determine the following PK parameters following LY900018 and GlucaGen administration, when possible:

Final, 01 Feb 2018 Page 12 of 26

Parameter	Units	Definition
AUC(0-4)	pmol.h/L	area under the concentration versus time curve from time zero to 4 hours post-dose
$AUC(0-t_{last})$	pmol.h/L	area under the concentration versus time curve from time zero to time t, where t is the last time point with a measurable concentration
$AUC(0-\infty)$	pmol.h/L	area under the concentration versus time curve from time zero to infinity
$\%$ AUC(t_{last} - ∞)	%	percentage of $AUC(0-\infty)$ extrapolated
C_{max}	pmol/L	maximum observed drug concentration
t_{max}	h	time of maximum observed drug concentration
$t_{1/2}$	h	half-life associated with the terminal rate constant (λz) in non-compartmental analysis
CL/F	L/h	apparent total body clearance of drug calculated after extra-vascular administration
V _z /F	L	apparent volume of distribution during the terminal phase after extra-vascular administration
V _{ss} /F	L	apparent volume of distribution at steady state after extra-vascular administration

The following PK parameters will also be calculated using baseline-adjusted (ie, change from baseline) concentrations of glucagon: AUC, C_{max} , and t_{max} . Baseline glucagon concentrations will be concentrations from samples obtained immediately prior to glucagon dosing (ie, predose).

Additional PK parameters may be calculated, as appropriate. The software and version used for the final analyses will be specified in the clinical study report. Any exceptions or special handling of data will be clearly documented within the final study report.

Formatting of tables, figures and abbreviations will follow the Eli Lilly Global PK/PD/TS Tool: NON-COMPARTMENTAL PHARMACOKINETIC STYLE GUIDE. The version of the tool effective at the time of PK analysis will be followed.

General PK Parameter Rules

- Actual sampling times will be used in the final analyses of individual PK parameters, except for non-bolus pre-dose sampling times which will be set to zero.
- C_{max} and t_{max} will be reported from observed values. If C_{max} occurs at more than one time point, t_{max} will be assigned to the first occurrence of C_{max} .
- AUC parameters will be calculated using a combination of the linear and logarithmic trapezoidal methods (linear-log trapezoidal rule). The linear trapezoidal method will be applied up to t_{max} and then the logarithmic trapezoidal method will be used after t_{max}. The minimum requirement for the calculation of AUC will be the inclusion of at least three consecutive plasma concentrations above the lower limit of quantification (LLOQ), with at least one of these concentrations following C_{max}.

Final, 01 Feb 2018 Page 13 of 26

- AUC(0-∞) values where the percentage of the total area extrapolated is more than 20% will be flagged. Any AUC(0-∞) value excluded from summary statistics will be noted in the footnote of the summary table.
- Half-life (t½) will be calculated, when appropriate, based on the apparent terminal loglinear portion of the concentration-time curve. The start of the terminal elimination phase for each subject will be defined by visual inspection and generally will be the first point at which there is no systematic deviation from the log-linear decline in plasma concentrations. Half-life will only be calculated when a reliable estimate for this parameter can be obtained comprising of at least 3 data points. If t½ is estimated over a time window of less than 2 half-lives, the values will be flagged in the data listings. Any t½ value excluded from summary statistics will be documented in the footnote of the summary table.
- A uniform weighting scheme will be used in the regression analysis of the terminal loglinear portion of the concentration-time curve.
- The parameters based on observed C_{last} will be reported.

Individual PK Parameter Rules

- Only quantifiable concentrations will be used to calculate PK parameters with the exception of special handling of certain concentrations reported below the lower limit of quantitation (BQL). Plasma concentrations reported as BQL will be set to a value of zero when all of the following conditions are met:
 - The compound is non-endogenous.
 - The samples are from the initial dose period for a subject or from a subsequent dose period following a suitable wash-out period.
 - The time points occur before the first quantifiable concentration.
- All other BQL concentrations that do not meet the above criteria will be set to missing.
- Also, where two or more consecutive concentrations are BQL towards the end of a profile, the profile will be deemed to have terminated and therefore any further quantifiable concentrations will be set to missing for the calculation of the PK parameters unless it is considered to be a true characteristic of the profile of the drug.

Individual Concentration vs. Time Profiles

- o Individual concentrations will be plotted utilizing actual sampling times.
- The terminal point selections will be indicated on a semi-logarithmic plot.
- o Baseline corrected concentration plots will also be presented

Average Concentration vs. Time Profiles

- The average concentration profiles will be graphed using scheduled (nominal) sampling times.
- o The average concentration profiles will be graphed using arithmetic average concentrations.
- o Quantifiable concentrations will be used to calculate average concentrations.

Final, 01 Feb 2018 Page 14 of 26

- \circ Concentrations at a sampling time exceeding the sampling time window specified in the protocol, or \pm 10%, will be excluded from the average concentration profiles.
- Concentrations excluded from the mean calculation will be documented in the final study report.
- O A concentration average will be plotted for a given sampling time only if 2/3 of the individual data at the time point have quantifiable measurements that are within the sampling time window specified in the protocol or ± 10%. An average concentration estimated with less than 2/3 but more than 3 data points may be displayed on the mean concentration plot if determined to be appropriate and will be documented within the final study report.

Treatment of Outliers during Pharmacokinetic Analysis

Application of this procedure to all pharmacokinetic analyses is not a requirement. Rather, this procedure provides justification for exclusion of data when scientifically appropriate. This procedure describes the methodology for identifying an individual value as an outlier for potential exclusion, but does not require that the value be excluded from analysis. The following methodology will not be used to exclude complete profiles from analysis.

Data within an Individual Profile

A value within an individual profile may be excluded from analysis if any of the following criteria are met:

• For any questionable datum that does not satisfy the above criteria, the profile will be evaluated and results reported with and without the suspected datum.

Data between Individual Profiles

- 1. If n<6, then the dataset is too small to conduct a reliable range test. Data will be analyzed with and without the atypical value, and both sets of results will be reported.
- 2. If n≥6, then an objective outlier test will be used to compare the atypical value to other values included in that calculation:
 - a. Transform all values in the calculation to the logarithmic domain.
 - b. Find the most extreme value from the arithmetic mean of the log transformed values and exclude that value from the dataset.
 - c. Calculate the lower and upper bounds of the range defined by the arithmetic mean $\pm 3*SD$ of the remaining log-transformed values.
 - d. If the extreme value is within the range of arithmetic mean $\pm 3*SD$, then it is not an outlier and will be retained in the dataset.
 - e. If the extreme value is outside the range of arithmetic mean $\pm 3*SD$, then it is an outlier and will be excluded from analysis.

If the remaining dataset contains another atypical datum suspected to be an outlier and $n \ge 6$ following the exclusion, then repeat step 2 above. This evaluation may be repeated as many times as necessary, excluding only one suspected outlier in each iteration, until all data remaining in the dataset fall within the range of arithmetic mean $\pm 3*SD$ of the log-transformed values.

Final, 01 Feb 2018 Page 15 of 26

Reporting of Excluded Values

Individual values excluded as outliers will be documented in the final report. Approval of the final report will connote approval of the exclusion.

